9.3.2.2 Safety Endpoints

The following endpoints will be used for all subjects:

- Occurrence, nature (Medical Dictionary for Regulatory Activities [MedDRA] preferred term), duration, intensity, relationship to vaccination, and whether the event led to early termination from the study, of any unsolicited systemic AEs reported within 30 minutes after each vaccination.
- Occurrence, time of onset, number of days of occurrence, intensity, action taken, and whether the reaction led to early termination from the study, of solicited (prelisted in the subject's diary card and CRB) injection site reactions occurring up to D07 after each vaccination.
- Occurrence, time of onset, number of days of occurrence, intensity, action taken, and whether the reaction led to early termination from the study, of solicited (prelisted in the subject's diary card and CRB) systemic reactions occurring up to D07 after each vaccination.

- Occurrence, nature (MedDRA preferred term), time of onset, duration, intensity, action taken, relationship to vaccination, and whether the event led to early termination from the study, of unsolicited AEs up to D30 after each vaccination.
- Occurrence, nature (MedDRA preferred term), time of onset, duration, seriousness criteria, relationship to vaccination, outcome, and whether the event led to early termination from the study, of SAEs (including AESIs) throughout the trial from Visit 1 up to the 6 month follow-up contact after the last vaccination.
- Occurrence, nature (MedDRA preferred term), time of onset, duration, intensity, action taken, relationship to vaccination, and whether the event led to early termination from the study for MAAEs throughout the trial from Visit 1 up to the 6 month follow-up contact after the last vaccination.

9.3.2.3 Safety Assessment Methods

At each visit, the Investigator or a delegate will perform a physical examination on the basis of relevant medical history according to the Investigator's clinical judgement and will ask the parent / guardian about any solicited reactions and unsolicited AEs recorded in the diary card, as well as about any other AEs that may have occurred since the previous visit. All relevant data will be transcribed into the CRB according to the instructions provided by the Sponsor.

9.3.2.3.1 Immediate Post-vaccination Observation Period

Subjects will be kept under observation for 30 minutes after each vaccination to ensure their safety. The post-vaccination observation should be documented in the source document. Any AE that occurs during this period will be noted on the source document and recorded in the CRB, as follows:

- Unsolicited systemic AEs will be recorded as immediate AEs in the CRB (presence marked as "yes" and details collected).
- Solicited and unsolicited injection site reactions and solicited systemic reactions will be recorded in the CRB in the same way as any reactions starting on the day of vaccination.
- SAEs will be recorded in the CRB and reported to the Sponsor in the same way as any other SAEs, according to the procedures described in [Section 10](#).

9.3.2.3.2 Reactogenicity (Solicited Reactions from Day 0 to Day 07 after Each Vaccination)

After each vaccination, parents / guardians will be provided with a diary card, a digital thermometer, and a flexible ruler, and will be instructed how to use them. The following items will be recorded by the subject's parent / guardian in the diary card on the day of vaccination and for the next 7 days (i.e., D0 to D07) until resolution:

- Daily temperature, with the route by which it was taken

- Daily measurement or intensity grade of all other solicited injection site and systemic reactions
- Action taken for each event (e.g., medication)

The action(s) taken by the parent or guardian to treat and/or manage any **solicited reactions** will be classified in the CRB using the following list (all applicable items should be checked):

- None
- Medication
- Health care provider contact
- Hospitalized
- Discontinuation of study vaccination

Parents / guardians will be contacted by telephone 8 days after each vaccination to remind them to record all safety information in the diary card.

If the timing of the telephone call should fall on a weekend or a holiday, the call should be made on the next business day. If contact is not made on the designated day, study staff will continue calling until contact is made. Every telephone attempt and its outcome will be documented in the source document.

[Table 9.1](#) and [Table 9.2](#) present, respectively, the injection site reactions and systemic reactions that are prelisted in the diary cards and CRB, together with the intensity scales.

Table 9.1: Solicited injection site reactions: terminology, definitions, and intensity scales

CRB term (MedDRA lowest level term [LLT])	Injection site tenderness	Injection site erythema	Injection site swelling
MedDRA preferred term	Injection site pain	Injection site erythema	Injection site swelling
Diary card term	Tenderness	Redness	Swelling
Definition	Pain when the injection site is touched or injected limb mobilized	Presence of a redness including the approximate point of needle entry	Swelling at or near the injection site Swelling or edema is caused by a fluid infiltration in tissue or cavity and, depending on the space available for the fluid to disperse, swelling may be either soft (typically) or firm (less typical) to touch and thus can be best described by looking at the size of the swelling
Intensity scale*	Grade 1: Minor reaction when injection site is touched Grade 2: Cries or protests when injection site is touched Grade 3: Cries when injected limb is mobilized, or the movement of the injected limb is reduced	Grade 1: > 0 to < 25 mm Grade 2: ≥ 25 to < 50 mm Grade 3: ≥ 50 mm	Grade 1: > 0 to < 25 mm Grade 2: ≥ 25 to < 50 mm Grade 3: ≥ 50 mm

* For the subjective reaction of tenderness, parents /guardians will record the intensity level (Grade 1, 2, or 3) in the diary card. For the measurable reactions of redness and swelling, they will record just the size of the reaction, and the classification as Grade 1, 2, or 3 will be assigned at the time of the statistical analysis. Since all subjects will be vaccinated before the second birthday, the same intensity scales will be used for all subjects.

Table 9.2: Solicited systemic reactions: terminology, definitions, and intensity scales*

CRB term (MedDRA LLT)	Fever	Vomiting	Crying Abnormal	Drowsiness	Appetite Lost	Irritability
MedDRA preferred term	Pyrexia	Vomiting	Crying	Somnolence	Decreased appetite	Irritability
Diary card term	Temperature	Vomiting	Abnormal crying	Drowsiness	Loss of appetite	Irritability
Definition	Elevation of temperature to $\geq 38.0^{\circ}\text{C}$ ($\geq 100.4^{\circ}\text{F}$)	Vomiting does not include spitting up	Inconsolable crying without a determined reason	Reduced interest in surroundings, or increased sleeping	See intensity scale	An excessive response to stimuli: increased fussiness, whining, and fretfulness despite attempts to comfort the infant and despite caregiver responses that would normally be soothing
Intensity scale†	Grade 1: $\geq 38.0^{\circ}\text{C}$ to $\leq 38.5^{\circ}\text{C}$ or $\geq 100.4^{\circ}\text{F}$ to $\leq 101.3^{\circ}\text{F}$ Grade 2: $> 38.5^{\circ}\text{C}$ to $\leq 39.5^{\circ}\text{C}$ or $> 101.3^{\circ}\text{F}$ to $\leq 103.1^{\circ}\text{F}$ Grade 3: $> 39.5^{\circ}\text{C}$ or $> 103.1^{\circ}\text{F}$	Grade 1: 1 episode per 24 hours Grade 2: 2–5 episodes per 24 hours Grade 3: ≥ 6 episodes per 24 hours or requiring parenteral hydration	Grade 1: < 1 hour Grade 2: 1–3 hours Grade 3: > 3 hours	Grade 1: Sleepier than usual or less interested in surroundings Grade 2: Not interested in surroundings or did not wake up for a feed / meal Grade 3: Sleeping most of the time or difficult to wake up	Grade 1: Eating less than normal Grade 2: Missed 1 or 2 feeds / meals completely Grade 3: Refuses ≥ 3 feeds / meals or refuses most feeds / meals	Grade 1: Easily consolable Grade 2: Requiring increased attention Grade 3: Inconsolable

*Since all subjects will be vaccinated before the second birthday, the same intensity scales will be used for all subjects.

†For all reactions but fever, parents / guardians will record the intensity level (Grade 1, 2, or 3) in the diary card. For fever, they will record the body temperature, and the classification as Grade 1, 2, or 3 will be assigned at the time of the statistical analysis based on the unit used to measure the temperature and the intensity scale.

Important notes for the accurate assessment of temperature:

Parents / guardians are to measure body temperature once per day, preferably always at the same time. The optimal time for measurement is the evening, when body temperature is the highest. Temperature is also to be measured at the time of any apparent fever. The observed daily temperature and the route of measurement are to be recorded in the diary card, and the highest temperature will be recorded by the site in the CRB. The preferred route for this study is rectal. Pre-vaccination temperature is also systematically collected by the investigator on the source document. Tympanic thermometers must not be used.

9.3.2.3.3 Unsolicited Adverse Events

In addition to recording solicited reactions, parents / guardians will be instructed to record any other medical events that may occur during the 30-day period after each vaccination. Space will be provided in the diary card for this purpose.

Information on SAEs will be collected and assessed throughout the study, from Visit 1 until 6 months after the last vaccinations. Any SAE occurring at any time during the study will be reported by the Investigator in the CRB according to the completion instructions provided by the Sponsor; this includes checking the “Serious” box on the AE CRF and completing the appropriate Safety Complementary Information CRF. All information concerning the SAE is to be reported either as part of the initial reporting or during follow-up reporting if relevant information became available later (e.g., outcome, medical history, results of investigations, copy of hospitalization reports. In case a subject experiences febrile convulsion (neurological event associating fever and seizure), the assessment will be performed according to the “Guideline for definition and collection of cases of febrile convulsion”, and this event will be considered an SAE.

See [Section 10](#) for further details on SAE reporting.

For each unsolicited AE (whether serious or non-serious), the following information is to be recorded:

- Start and stop dates^a
- Intensity of the event:

For measurable unsolicited AEs that are part of the list of solicited reactions, the size of the AE as well as the temperature for fever will be collected and analyzed based on the corresponding scale used for solicited reactions (see [Table 9.1](#) and [Table 9.2](#)).

All other unsolicited AEs will be classified according to the following intensity scale:

^a The stop date of all related AEs will be actively solicited. For other events, the investigator will provide the stop date when it becomes available. AEs for which no stop date was obtained during the course of the study will be considered as ongoing at the end of the study.

- Grade 1: A type of adverse event that is usually transient and may require only minimal treatment or therapeutic intervention. The event does not generally interfere with usual activities of daily living.
- Grade 2: A type of adverse event that is usually alleviated with additional therapeutic intervention. The event interferes with usual activities of daily living, causing discomfort but poses no significant or permanent risk of harm to the research participant.
- Grade 3: A type of adverse event that interrupts usual activities of daily living, or significantly affects clinical status, or may require intensive therapeutic intervention.
- Whether the AE was related to the investigational product (for unsolicited systemic AEs)

The Investigator will assess the causal relationship between the AE and the investigational product as either “Not related” or “Related,” as described in [Section 9.3.2.3.6](#).

- Action taken for each AE (e.g., medication)

The action(s) taken by the parent or guardian to treat and/or manage any unsolicited AEs will be classified in the CRB using the following list (all applicable items should be checked):

- None
- Medication
- Health care provider contact
- Hospitalized
- Discontinuation of study vaccination
- Whether the AE was serious
- Whether the AE caused study discontinuation

9.3.2.3.4 Adverse Events of Special Interest

An AESI is defined as an event for which ongoing monitoring and rapid communication by the Investigator to the Sponsor must be done. The following AEs will be captured as AESIs throughout the study:

- Generalized seizures (febrile and non-febrile) ([54](#)) ([55](#))
- Kawasaki disease ([55](#)) ([56](#)) ([57](#))
- Guillain-Barré syndrome ([56](#))
- Idiopathic thrombocytopenic purpura (ITP) ([57](#)) ([58](#))

These events have been listed as AESIs based on the feedback received from the European Union regulators.

No safety concerns relating to these AESIs have been identified with the use of MenACYW conjugate vaccine in the completed clinical trials. Because of their medical importance and to ensure expedited communication to the Sponsor, these AESIs are to be considered and collected as SAEs and reported to the Sponsor according to the procedure described in [Section 10](#). Further instructions on the data collection for these events and the relevant definitions will be provided in the Operating Guidelines.

9.3.2.3.5 Medically-Attended Adverse Events

MAAE information will be collected throughout the study. MAAEs will be recorded as unsolicited AEs for up to D30 after each vaccination and as MAAEs until the next study visit on the appropriate diary cards. MAAEs that occur from D31 after the last vaccination visit until the 6-month follow up phone call will be recorded in the appropriate memory aid. An MAAE that occurs within the study period but meets the definition of an SAE should be reported only on the SAE Reporting Form but not on the MAAE page of the CRB. The Investigator will assess the causal relationship between the MAAE and the investigational or study product as either “Not related” or “Related”, as described in [Section 9.3.2.3.6](#).

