Unsolicited AE / AR:

An unsolicited AE is an observed AE that does not fulfill the conditions prelisted in the CRB in terms of diagnosis and/or onset window post-vaccination. For example, if vomiting between D0 and D07 is a solicited reaction (i.e., prelisted in the protocol and CRB), then a vomiting starting on D07 is a solicited reaction, whereas vomiting starting on D08 post-vaccination is an unsolicited AE. Unsolicited AEs includes both serious (SAEs) and non-serious unsolicited AEs.

Injection Site Reaction:

An injection site reaction is an AR at and around the injection site. Injection site reactions are commonly inflammatory reactions. They are considered to be related to the product administered.

Systemic AE:

Systemic AEs are all AEs that are not injection or administration site reactions. They therefore, include systemic manifestations such as vomiting, fever, as well as localized or topical manifestations that are not associated with the vaccination or administration site (e.g., erythema that is localized but that is not occurring at the injection site).

Adverse Event of Special Interest (AESI):

An AESI is an event for which ongoing monitoring and rapid communication by the Investigator to the Sponsor must be done. Such an event might warrant further investigation in order to characterize and understand it. Depending on the nature of the event, rapid communication by the study Sponsor to other parties (e.g., regulators) might also be warranted.

Medically-Attended Adverse Event (MAAE)

An MAAE is defined, for the purpose of this study, as a new onset of a condition that prompts the subject or subject's parent/guardian to seek unplanned medical advice at a health care provider's office or Emergency Department. This definition excludes pre-planned medical office visits for routine pediatric check-ups or follow-up visits of chronic conditions with an onset prior to entry in the study. Health care provider contact made over the phone or by email will be considered a physician office visit for the purpose of MAAE collection. The outcome of the health care provider contact (whether it results in a prescription or not) will not be considered as a basis for reporting the event as an MAAE and all contacts should be reported. Sufficient data should be collected for the event to allow an assessment of the causality and diagnosis, if possible.

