4.3.1.3.5 Medically-Attended Adverse Events

MAAE information will be collected throughout the study. MAAEs will be recorded as unsolicited AEs for up to D30 after each vaccination and as MAAEs until the next study visit on the appropriate diary cards. MAAEs that occur from D31 after the last vaccination visit until the 6-month follow up phone call will be recorded as such in the appropriate memory aid. An MAAE that occurs within the study period but meets the definition of an SAE should be reported only on the SAE Reporting Form. The Investigator will assess the causal relationship between the MAAE and the investigational or study product as “Not related” or “Related”.

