4.4.2.4 Medically-Attended Adverse Event (MAAE)

An event will be considered as an MAAE if “Yes” is checked for “Is the event an MAAE?” in the CRF.

MAAEs will be analyzed throughout the study using the following periods:

- During the entire study period after any dose from D0 to last phone call (i.e., all MAAEs that occurred during the study)
- From Day 0 to Day 30 after each vaccination

A MAAE with missing time of onset will be considered to have occurred just after the vaccination indicated by the visit number, so will be included in the safety analysis tables mentioned above.

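### The protocol routes serious medically-attended events away from the MAAE page and the SAP counts only flagged MAAEs, so unless the flag is also completed for SAEs the MAAE tables omit events that the MAAE definition includes

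*Protocol*

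**What the plan says.** **Definition and endpoint.** Protocol 9.3.2.1 defines an MAAE as "a new onset of a condition that prompts the subject or subject's parent/guardian to seek unplanned medical advice" at a provider's office or Emergency Department. It excludes planned routine visits and follow-up of chronic conditions that predate the study. Seriousness is not an exclusion. Protocol 9.3.2.2 makes MAAEs an endpoint from Visit 1 to the 6-month contact, again with no exclusion for seriousness.

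**Collection.** Protocol 9.3.2.3.5 says that an MAAE that meets the SAE definition "should be reported only on the SAE Reporting Form but not on the MAAE page of the CRB". SAP 4.3.1.3.5 keeps part of this rule (an MAAE that "meets the definition of an SAE should be reported only on the SAE Reporting Form") but drops the words about the MAAE page. Protocol 9.3.2.3.4 adds that, for the listed events of special interest, "these AESIs are to be considered and collected as SAEs". Under Protocol 9.3.2.3.3, an SAE is recorded by ticking the Serious "box on the AE CRF and completing the appropriate Safety Complementary Information CRF".

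**Derivation.** SAP 4.4.2.4 states: "An event will be considered as an MAAE if “Yes” is checked for “Is the event an MAAE?” in the CRF". It describes the whole-study analysis as covering "all MAAEs that occurred during the study", and it also has a Day 0 to Day 30 analysis after each vaccination. SAEs and AESIs are derived from their own CRF items in SAP 4.4.2.3.

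**The concern.** The endpoint, the collection rule and the derivation do not fit together. By definition a serious event that leads to unplanned medical advice is an MAAE, and the collection rule itself calls it one. The same rule then keeps it off the MAAE page, and the analysis counts only what carries the MAAE flag. If the flag follows the page, a table presented as all MAAEs contains only the non-serious ones. A generalized seizure seen in an Emergency Department would be left out, because AESIs are collected as SAEs.

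Describing safety is the whole of the observational objectives, so a reported rate should measure what its definition says. A reader comparing MAAE percentages between vaccines, or with another study that counts serious events, could not tell that they had been left out. If the rule is silent and sites complete the item differently, the count would also depend on site practice.

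**Working it through.** The documents state no MAAE or SAE incidence, so there is no figure to reproduce. The check is first textual, then a bound on the size.

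**Step 1: follow one event through the plan.** Take a new-onset condition that leads to an unplanned Emergency Department visit and then to hospital admission.

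| Stage | Source | Result |
|---|---|---|
| Is it an MAAE? | Protocol 9.3.2.1 | Yes; seriousness is not an exclusion |
| Is it an SAE? | Protocol 9.3.2.1 | Yes; inpatient hospitalization |
| Entered on the MAAE page? | Protocol 9.3.2.3.5 | No |
| MAAE item completed on its AE CRF record? | No section of either document | Not stated |
| Counted as an MAAE? | SAP 4.4.2.4 | Only if that item is Yes |
| Added back by another rule? | SAP 4.4.2.3, 4.4.2.4, 5.7 | No |
| Counted as an SAE? | SAP 4.4.2.3 | Yes, over the whole study |

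Everything turns on the fourth row. On the plainest reading of the collection rule the item is left blank, but the documents do not settle it.

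**Step 2: size, if serious events are not flagged.** Let S be the set of subjects with at least one serious MAAE (proportion s) and M the set with at least one flagged non-serious MAAE (proportion m).

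- Incidence by the definition: P(S or M). Incidence as counted: P(M) = m.
- Understatement: P(S and not M), the proportion of subjects whose only MAAEs were serious.
- Upper bound: min(s, 1 − m). Under independence: s × (1 − m).
- It is 0 if every subject in S is also in M, and 0 if SAEs are flagged after all.

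The values of s and m below are assumptions. The enrolled numbers, 435 per infant group and 100 per toddler group, are from Protocol 12.5 and the Synopsis.

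| s | m | s × (1 − m), points | Of 435 | Of 100 | Upper bound, points |
|---|---|---|---|---|---|
| 0.5% | 70% | 0.005 × 0.30 = 0.15 | 0.7 | 0.15 | 0.5 |
| 1% | 50% | 0.01 × 0.50 = 0.50 | 2.2 | 0.5 | 1.0 |
| 3% | 50% | 0.03 × 0.50 = 1.50 | 6.5 | 1.5 | 3.0 |
| 5% | 20% | 0.05 × 0.80 = 4.00 | 17.4 | 4.0 | 5.0 |

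Over s = 0.5% to 5% and m = 20% to 70%, the understatement under independence is 0.15 to 4.0 points. Throughout that range 1 − m exceeds s, so the upper bound is s itself.

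**Step 3: event counts.** SAP Table 5.1 also reports numbers of events for unsolicited AEs. An MAAE event count would fall by every unflagged serious MAAE, whether or not the subject had another flagged event.

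**The case against.** The strongest objection is that the omission is not proven. The SAP counts a CRF item, not entries on an MAAE page, and several passages suggest that the item could sit on the common AE record:

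- SAEs are entered on the AE CRF (Protocol 9.3.2.3.3 and 10.1), and information on MAAEs, SAEs and AESIs from the 6-month call is transcribed to that same form (Protocol 11.1).
- AESIs are collected as SAEs and still have their own item (SAP 4.4.2.3), so a second flag on a serious event is already normal.
- SAP 4.4.2.2.4 treats serious, AESI and MAAE as separate attributes of an unsolicited event.
- SAP 4.3.1.3.5 drops the words about the MAAE page.

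This stands. A reader might infer that every serious MAAE is certainly missing, but the documents do not support that, because they do not say how the item is completed for an SAE. What does not follow is that the plan is adequate as it is: the silence leaves the content of the table undetermined.

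Four further points on the other side also stand:

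- A reader might conclude that the most severe events are lost. Protocol 9.3.2.1 separates serious from severe, and Grade 3 non-serious MAAEs are counted on any reading.
- A reader might conclude that safety information disappears. It does not. SAP 4.4.2.3 tabulates all SAEs and AESIs within 7 days, within 30 days and over the whole study. This does not repair the MAAE percentage, though: adding SAE and MAAE percentages does not give a subject-level incidence, since a subject can be in both.
- Not every SAE is an MAAE. An exacerbation of a chronic condition that predates the study can be serious without being a new onset, so putting SAE incidence in place of s would overstate the effect.
- The analysis is descriptive (SAP 5.1.3) and the same rule applies in every group, so no test or power figure is affected and nothing shows a biased comparison between vaccines.

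Single reporting of SAEs is a reasonable way to avoid duplicate entry and need not change.

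**Conclusion.** The point holds in conditional form. The collection rule sends serious MAAEs away from the MAAE page, the SAP relies on the MAAE item alone, and no rule adds medically attended SAEs back, although the definition and endpoint include them. Unless the item is nevertheless completed for SAEs, the MAAE tables omit serious MAAEs, including medically attended AESIs, while being described as complete.

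The understatement of subject-level incidence lies between 0 and the proportion of subjects whose only MAAE was serious. The 0.15 to 4.0 point illustration rests on assumed rates and on independence between serious and non-serious MAAEs; neither comes from the documents. If children with a serious event tend also to have other flagged MAAEs, the figure is smaller. The matter concerns the accuracy and labelling of a descriptive safety endpoint. It does not touch the immunogenicity conclusions, and the serious events are still reported as SAEs.

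**What to change.** Reconcile Protocol 9.3.2.3.5, SAP 4.3.1.3.5 and SAP 4.4.2.4:

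1. State in the collection rule that SAEs keep their single reporting route, but that the MAAE item is answered for every SAE.
2. In SAP 4.4.2.4, define MAAEs for analysis as all flagged events plus any SAE that meets the Protocol 9.3.2.1 definition (new onset and unplanned medical advice).
3. Where the item was not completed for an SAE, use the action-taken entries for provider contact or hospitalization only to find candidates for review, done blind to vaccine group. Those entries show neither new onset nor whether the contact was unplanned, so they should not decide the classification by themselves.
4. If serious events are to stay out, title the tables *non-serious MAAEs* and add a subject-level row for *MAAE or SAE*, counting each subject once.

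The cost is one derivation line or one table row, plus a short review of candidate SAEs if the item was left blank. The reported MAAE incidence may become slightly higher. Action taken is already recorded for each AE, so the candidate search needs no new data item.
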